7.7 SECONDARY ANALYSES

7.7.1 OS from the start of afatinib until the date of death

OS is defined as the time from the start of afatinib until death for any reason. Subjects who have not died at the time of the statistical analysis will be censored at the time they were last known contact.

OS will be analyzed in a similar fashion with primary analysis. Analysis will be provided for population set TS.

The swimlane plot of overall survival by subsequent treatment will be provided.

For the purposes of displaying the subsequent treatment duration in plot, incomplete second line treatment start/end and third line treatment start dates will be imputed as below:

If month and year are present and day is missing for treatment start date:

Proprietary confidential information © 2024 Boehringer Ingelheim International GmbH or one or more of its affiliated companies

- Set day to the first day of month

If month and year are present and day is missing for treatment end date:

- If year=year of treatment start date and
 - If month = month of treatment start date then set day to last day of month
 - If month > month of first dose then set day to first day of month

For all other cases, the missing dates will not be imputed and partial dates will not be displayed on plot.

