- If year > year of first dose then set day to first day of month

For all other cases, the missing dates will not be imputed and the subject will censored at last known of contact date and censored situation will be missing treatment end date.

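### SAP 7.7.1 leaves some second-line end dates with known month and year off the swimlane plot, because the partial-date rule has no later-year branch and one line tests the wrong start date

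*SAP*

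**What the plan says.** SAP 7.7.1 plans a descriptive display: "The swimlane plot of overall survival by subsequent treatment will be provided". It then limits the purpose of the date rules that follow: "For the purposes of displaying the subsequent treatment duration in plot, incomplete second line treatment start/end and third line treatment start dates will be imputed".

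For an end date with month and year present and day missing, the rule has one condition on the year, "If year=year of treatment start date and", with two lines under it:

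- Same month: "If month = month of treatment start date then set day to last day of month".
- Later month: "If month > month of first dose then set day to first day of month".

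Whatever is left falls to the closing sentence: "For all other cases, the missing dates will not be imputed and partial dates will not be displayed on plot".

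The matching rule for the afatinib end date in SAP 7.6 has a further line: "If year > year of first dose then set day to first day of month".

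**The concern.** Two things look like slips in adapting the rule from another section. No line covers an end date in a calendar year after the second-line start year, although the month and year are known. And the reference date changes between two adjacent lines, from the treatment start date to the first dose. In SAP 7.6 and 7.10.1 the first dose is the first dose of afatinib, so the literal test compares the second-line end month with a month that may belong to an earlier year.

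At stake is the accuracy of the drawn second-line durations. The Protocol (9.1) collects data on subsequent therapy, and with at most 76 patients a few incomplete lanes change how the plot looks. The SAP does not say how a lane with an undrawn end should appear, so a reader could take it for treatment still ongoing. Two programmers could also read the first dose differently and produce different plots.

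**Working it through.** **No document figure to reproduce.** The point concerns date logic. The documents state no missing-day rate and no second-line duration.

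**1. The SAP's partial-date rules side by side (month and year known, day missing).**

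| Rule | Date in a later year |
|---|---|
| SAP 7.2, medication end | last day of month, whatever the year |
| SAP 7.6, afatinib end | first day of month |
| SAP 7.10.1, AE onset | first day of month |
| SAP 7.7.1, second-line end | no branch; not imputed, not drawn |

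SAP 7.7.1 is the exception, and no reason is given.

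**2. The literal rule on examples (end day missing).**

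- Second line December 2021 to January 2022: the end year differs from the start year, so the date is not drawn, although the course is short.
- Second line January to December 2022, afatinib begun in any month but December: the end year equals the start year and December is later than the first-dose month, so the date is drawn, although the course is long.
- Afatinib from September 2020, second line February to June 2021: same year; June is not February, and June (6) is not later than September (9). The date is not drawn, only because of the reference date.

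**3. Share of courses ending in a later year, by length.** With the start month spread evenly over the year and a length of d whole months, the share is min(d, 12)/12: 1 month 8%, 3 months 25%, 6 months 50%, 9 months 75%, 11 months 92%, 12 months or more 100%.

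**4. Without a study cut-off.** With exponential duration and λ = ln 2/median, P(later year) = (1 − exp(−12λ))/(12λ). For a median of 6 months, 12λ = 1.386 and the result is 0.75/1.386 = 54%. For 10 months, 0.565/0.832 = 68%. For 12 months, 0.5/0.693 = 72%. These ignore the end of data collection, after which long courses are still ongoing and have no end date to impute.

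**5. Within the study window.** Inputs from the Protocol: enrolment May 2020 to December 2021 (taken as uniform), data collection to December 2023 (Milestones; 9.2.2), and exponential TOT with median 12 months (9.5). Assumed: second line starts when afatinib stops, exponential second-line duration with a median of 4 to 15 months, and first dose read as first afatinib dose. There were 400,000 draws per row, and only courses ending by December 2023 were kept. Shares are of end dates that lack the day.

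| Assumed second-line median | Lost: later year | Lost: wrong reference | Total lost | Later-year losses under 12 months long | Longest quarter lost |
|---|---|---|---|---|---|
| 4 months | 38% | 24% | 62% | 76% | 88% |
| 6 months | 47% | 20% | 68% | 64% | 97% |
| 10 months | 57% | 16% | 74% | 51% | 100% |
| 15 months | 63% | 14% | 77% | 45% | 100% |

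Totals are taken before rounding (for 6 months, 47.4% + 20.3% = 67.7%). Median length of the later-year losses is 7.8, 9.8, 11.8 and 12.9 months down the rows. For the wrong-reference losses it is 2.4 to 3.0 months, and for the courses still drawn 2.0 to 3.1 months.

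**6. After correction.** With a later-year branch and the month test tied to the second-line start, every end date with month and year present is imputed: 0% lost.

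**The case against.** The case against giving this weight is strong on consequence.

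- **Scope.** Complete end dates are drawn whatever the length, and ongoing courses have no end date. Only dates lacking the day are touched, and nobody can say from the documents how many there will be. This stands.
- **What is lost.** The text withholds a partial date from the plot. It does not remove the patient or the survival lane. SAP 7 also lists the raw eCRF data, so the partial date stays visible there. This stands.
- **Estimates.** OS runs to death: "OS is defined as the time from the start of afatinib until death for any reason". Neither it nor TOT or ORR uses the rule, and second-line duration is not a listed outcome. This stands.

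A reader might infer that the longest second-line treatments drop out of the plot. The documents do not support that. The trigger is crossing a calendar year, which goes with length but is not the same thing: between 45% and 76% of the later-year losses in the table lasted under 12 months, and the reference-date slip removes short same-year courses.

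A reader might also infer that this plot is the only planned look at what follows the switch. SAP 7.8.1 summarises resistance mechanisms after afatinib, Kaplan-Meier OS includes survival after the switch, and gaps in the section numbering of the public documents prevent a firm statement.

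Nor is it a fault that the start-month line uses the last day and the later-month line the first. In the start month, the last day keeps the end from falling before a known start.

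What the objection does not remove is that a rule written to use partial dates discards dates whose month and year are known, where the SAP's parallel rules keep them.

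**Conclusion.** The point holds as a certain but small defect in the SAP text. Followed literally, SAP 7.7.1 leaves undrawn every missing-day second-line end date in a later calendar year, and some in the same year. This includes every such course of 12 months or more and many shorter ones. The 62% to 77% range applies only to end dates without a day, and rests on assumed second-line medians of 4 to 15 months, uniform enrolment, an immediate switch, and the afatinib reading of first dose. If first dose is read as the second-line start, only the later-year loss of 38% to 63% remains. No count of patients can be given. The effect is confined to drawn second-line duration in one descriptive plot.

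**What to change.** In SAP 7.7.1, for a second-line end date with month and year present and day missing:

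1. Add a later-year branch: when the end year is after the second-line start year, use the first of the month, as SAP 7.6 does for afatinib.
2. In the later-month line, replace the first dose with the second-line treatment start date.
3. Keep the last-day rule for the start month. A single first-of-month convention for all branches could place the end before a known start.
4. Cap the imputed end at death, third-line start or last contact, but not before the second-line start. The cap matters mainly for the last-day rule.
5. State how a lane with an end date that is still unknown is marked, so that it is not read as ongoing treatment.

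The cost is a few lines of SAP wording and plot programming. No estimate changes and no new data are needed.

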7.7.2 ORR according to RECIST 1.1[\[1\]](#) with afatinib in first-line treatment

ORR defined as percentage of subjects with a best overall response of CR or PR according to RECIST 1.1. Response is only recorded when RECIST 1.1 criteria is used.

The best overall response (BOR) calculated based on the overall visit responses from each RECIST assessment during first-line treatment period (defined as start of afatinib to start of second-line treatment). It is the best response a subject has had during first-line treatment period, from start of afatinib until earliest RECIST progression (PD or death) or the last evaluable assessment in the absence of RECIST progression (PD or death).

Categorization of BOR will be based on the RECIST 1.1[\[1\]](#) criteria using the following response categories: CR, PR, stable disease (SD), progressive disease (PD) and not evaluable (NE) (CR>PR>SD>PD>NE). For subjects whose progression event is death, BOR will be calculated based on data up until the last evaluable RECIST assessment prior to death. If no evaluable RECIST assessments prior to death, then BOR will be assigned as PD.

To be assigned a status of SD, follow-up disease assessment must have met the SD criteria at least once after first dose at a minimum interval of 42 days. If the minimum time for SD is not met, best response will depend on the subsequent assessments. For example, if an assessment of PD follows the assessment of SD and SD does not meet the minimum time requirement the best response will be PD. Alternative patients lost to follow-up after an SD assessment not meeting the minimum time criteria will be considered NE.

Progression events that have been censored due to start second line treatment or other subsequent treatments before reporting PD after the last evaluable assessment will not contribute to the BOR derivation.

The Clopper-Pearson method[\[2\]](#) will be used to provide an estimation of ORR with 95% Cis. BOR will analyzed in terms of frequency and proportions. All those analyses will be performed on the Treated Set (TS).

7.8 OTHER ANALYSES

7.8.1 Resistance mechanisms

Type and proportion of Resistance mechanisms (T790M, etc.) after afatinib first-line treatment will be summarized for Treated Set (TS).

Proprietary confidential information © 2024 Boehringer Ingelheim International GmbH or one or more of its affiliated companies

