Name of finished medicinal product: Giotrif®				
Name of active ingredient: Afatinib				

withdraw before the end of study will be censored at the time of last known contact.
 
Secondary outcomes
 
Overall survival (OS) from the start of afatinib until the date of death, loss to follow up (including patient withdrawal) or end of study period
 
Objective response rate (ORR), [objective response is defined as best overall response of complete response (CR), partial response (PR)] according to RECIST 1.1 with afatinib first-line therapy
 
Adverse events (AEs), serious adverse events (SAEs), afatinib-related AEs (ADRs) as indicated by incidence, seriousness and intensity graded according to United States (US) national cancer institute's (NCI) common terminology criteria for AEs version 5.0 (CTCAE Version 5.0)
 
Further outcome
 
Resistance mechanisms (Type and proportion:T790M,etc) after afatinib first-line treatment.
				
Data sources:	
Data for this study will be obtained via the following sources:
 
- Patient medical information: The investigator or authorized medical staff will record clinical and treatment data from patients' medical records into an electronic case report form (eCRF) at baseline and at every visit up to end of the follow up period (refer to Section 9.4)			
Study size:	76 patients			
Study duration:	The duration of data collection for an individual patient will be a maximum of approximately 33 months, It is anticipated that all data collection for this study started from May 2020(first patient enrolled) and will continue until December 2023 (two years after the last patient was enrolled)			
Data analysis:	
Time on treatment (TOT) will be analysed using Kaplan-Meier method, and the median Time on Treatment (TOT) along with two-sided 90% confidence interval (CI) will be calculated. Overall survival (OS) will be analysed similarly.
 
Objective response rate (ORR) and acquired resistance mutation type, and AEs will be summarised descriptively by frequency and proportions.
			
Milestones:				
IRB/IEC Approval: May 2020				
First Patient In: May 2020				

Name of company: Boehringer Ingelheim		
Name of finished medicinal product: Giotrif®		
Name of active ingredient: Afatinib Last Patient In: Dec 2021 Interim Analysis: Dec 2022 Last Patient Out: Dec 2023 Database Locked: Mar 2024 Final NIS Report: Jun 2024		

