9.7 DATA ANALYSIS

For the purpose of this study, analyses will generally be descriptive in nature and will be conducted using SAS statistical software (version 9.3 or higher). Descriptive data regarding patient demographic and clinical characteristics will be calculated. For categorical measures, data will include the frequency (number of cases (n)) and percentage (%) of total study

patients observed in each category (N). All variables will be summarised descriptively through tabular displays of mean, median, ranges and standard deviations of continuous variables and frequency distributions of categorical variables. When necessary, continuous variables also will be categorised into intervals, with the distribution of patients (n, N, %) for each interval provided.

[figure not shown]
AEs will be graded in accordance with CTCAE Version 5.0. The safety analyses include frequency and intensity of AEs, SAEs and ADRs by System Organ Class (SOC)/Preferred Term (PT) using a current medical dictionary for regulatory activities (MedDRA) dictionary. In addition, AEs resulting in the discontinuation of treatment will be studied.

To assess the presence of channelling bias, we will use the data from study 1200-0066 to assess potential channelling and to put the results into perspective. The baseline characteristics of patients in this study and in study 1200-0066 separately. Patient characteristics will be compared between the two groups using absolute standardised differences (ASD), where an ASD of at least 10% will be considered a meaningful difference.

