6.6 HANDLING OF MISSING DATA AND OUTLIERS

The details of imputation for partial and missing data for date of adverse event and concomitant therapy are stated at [section 7.10.1](#) and [7.2](#) below, respectively. The details of imputation for partial and missing data for date of TOT event and OS event are stated at [section 7.6](#) and [7.7.1](#) below, respectively. Other missing data will be recorded as missing/unknown, and no other imputation of missing data will be performed unless otherwise stated.

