7. PLANNED ANALYSIS

Continuous data will be summarized in terms of the mean, standard deviation, median, minimum, maximum and number of observations, unless otherwise stated. The minimum and maximum will be reported to the same number of decimal places as the raw data recorded in the database. The mean, median will be reported to one more decimal place than the raw data recorded in the database. The standard deviation will be reported to two more decimal places than the raw data recorded in the database. In general, the maximum number of decimal places reported shall be four for any summary statistic.

Categorical data will be summarized in terms of the number of subjects providing data at the relevant time point (n), frequency counts and percentages. Percentages will be presented to one decimal place. Percentages will not be presented for zero counts. The category missing will be displayed only if there are actually missing values. When necessary, continuous variables also will be categorized into intervals, with the distribution of patients (n, N, %) for each interval provided.

Confidence intervals will be presented to one more decimal place than the raw data.

Raw data collected in eCRF will also be listed.

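### Does SAP 7.8.1 need to state the percentage denominator for resistance mechanisms?

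*SAP*

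**What the plan says.** SAP 7.8.1 is a single sentence: "Type and proportion of Resistance mechanisms (T790M, etc.) after afatinib first-line treatment will be summarized for Treated Set (TS". The Treated Set (SAP 6.3) requires only one documented dose of first-line afatinib, with no genetic test afterwards.

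The general rules that bear on the denominator are these:

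- SAP section 7 summarises categorical data "in terms of the number of subjects providing data at the relevant time point (n), frequency counts and percentages", and adds: "The category missing will be displayed only if there are actually missing values". It also has the raw eCRF data listed.
- SAP 6.6: "Other missing data will be recorded as missing/unknown, and no other imputation of missing data will be performed unless otherwise stated".
- Protocol 9.7 says that for categorical measures "data will include the frequency (number of cases (n)) and percentage (%) of total study" "patients observed in each category (N"). The sentence just before it reads: "Descriptive data regarding patient demographic and clinical characteristics will be calculated".
- Protocol section 4 (Abstract): "Objective response rate (ORR) and acquired resistance mutation type, and AEs will be summarised descriptively by frequency and proportions".

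On testing itself, Protocol 4.1 collects genetic reports only where they exist (footnote b) and ties testing before the next line of treatment to clinical practice (footnote f). Protocol 9.2.4 makes testing after progression optional, and Protocol 9.4 mandates no tests. Protocol section 8 makes resistance an exploratory objective, framed as collecting data.

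**The concern.** A patient without a genetic test after afatinib cannot contribute a resistance mechanism. The Treated Set can contain several kinds of such patient: those still on afatinib at study end (a case that SAP Table 7.6: 1 provides for), those who die or are lost first, and those whose physician does not retest. If the whole Treated Set is the base, each of them counts as though the mechanism were absent. The percentage then mixes how often patients were retested with how often the mechanism was found.

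The risk is one of interpretation. Protocol sections 4 and 7 cite T790M in more than 50% of patients with resistance to first- or second-generation agents. A diluted study figure placed beside that could be taken for a lower T790M rate when it only reflects less testing. Nor does the text fix the base: two programmers could each follow 7.8.1 and print different percentages.

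**Working it through.** The plan gives no target, interval or sample size for resistance, so there is no figure of its own to reproduce. The check has two parts.

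**1. How large could the dilution be?**

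Inputs:

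- Treated Set N = 76. This is the planned size in Protocol 9.5, taken as the maximum.
- p = share positive among tested patients. Assumed 40% to 60%; the protocol's background puts T790M above 50%.
- n = number tested after afatinib. The documents give none, so 20, 40 and 60 are assumed.

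Formula: Treated Set percentage = p × n / 76.

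| Tested n | n/76 | p = 40% | p = 50% | p = 60% |
|---|---|---|---|---|
| 20 | 26.3% | 8/76 = 10.5% | 10/76 = 13.2% | 12/76 = 15.8% |
| 40 | 52.6% | 16/76 = 21.1% | 20/76 = 26.3% | 24/76 = 31.6% |
| 60 | 78.9% | 24/76 = 31.6% | 30/76 = 39.5% | 36/76 = 47.4% |

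The same 31.6% arises from 24/60 = 40% and from 24/40 = 60%, so a Treated Set percentage with nothing beside it would be ambiguous. If all 76 are tested, or if n is the base, there is no dilution.

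**2. Would the table leave that percentage with nothing beside it?**

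Section 7.8.1 sits under SAP section 7, so the section 7 rules apply. The table then shows n with data, the count per mechanism and, where results are absent, a missing row. Take the case of 40 tested and 20 positive:

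- Base = n with data: 20/40 = 50.0%, with 36 (= 76 − 40) shown as missing.
- Base = Treated Set: 20/76 = 26.3%, with n = 40 and the same 36 shown. The reader recovers 20/40 = 50.0%.

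The ambiguous case also separates: 24/76 appears with n = 60 in one study and n = 40 in the other.

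**3. Which base does the text favour?**

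- SAP 7.8.1 says whose data enter the table. That is an analysis set, not a percentage base.
- SAP section 7 puts the number providing data directly beside the percentages. Percentages on n are a natural reading, though not stated.
- Protocol 9.7 leans towards all study patients, but the sentence before it is about demographic and clinical characteristics.
- The Abstract gives no denominator. Grouping resistance with ORR and adverse events shows a shared analysis set at most.
- The words type and proportion in 7.8.1 can also mean the distribution of the mechanisms found, which untested patients do not dilute.

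The base is therefore unspecified in the visible text, and a Treated Set base is not the more likely reading.

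**The case for a change.** The strongest case for a change is that it would cost one sentence and need no new data. The dilution identity is exact, its direction is certain if the Treated Set is the base and anyone is untested, and no visible passage says which base applies. ORR has its own category for unevaluable patients in SAP 7.7.2, while 7.8.1 names no row for the untested. A missing row can also sit inside a percentage based on all treated patients, so the general rules do not force the tested-only base.

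All of that stands as description. Three things limit it.

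- The general missing row does the work of a not-tested row. It lumps patients still on afatinib with patients off treatment and not retested, but the raw-data listings allow them to be separated.
- A tested-only percentage is not clean either. Testing follows clinical practice, so the tested group is selected, and it is small: 95% Clopper-Pearson limits are 27.2% to 72.8% for 10/20, 33.8% to 66.2% for 20/40 and 36.8% to 63.2% for 30/60.
- The documents in hand are incomplete here. The protocol's contents go from 9.7.1 to 9.7.3, and the SAP history table moves resistance mechanisms out of the secondary outcomes, citing a section 5.3 that the public copy lacks. Text absent from the public copy cannot be counted as missing from the plan.

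**Conclusion.** No change is needed. This is a gap in detail that analysts will fill sensibly. SAP 7.8.1 leaves the percentage base open, but the section 7 display rules put the number with data and the number missing in the same table, so either base yields the tested-only share. Under the assumptions shown (76 treated, 40% to 60% positive among 20 to 60 tested), a Treated Set percentage could read anywhere from 10.5% to 47.4%. That spread affects how one exploratory figure is labelled. It changes no test, no planned interval and no sample size, and time on treatment, overall survival, ORR and safety are untouched.

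This rests on the section 7 rules being applied to 7.8.1 and on genetic results being among the eCRF data listed. The retest numbers are illustrative, because the documents give none. Whoever builds the table would ordinarily label the base as patients with a genetic result after afatinib and note that they are a selected group; that is table labelling, not an amendment.
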